6.2 Discussion of the Study Design, Including the Choice of Control Groups

The objective of this non-inferiority study is to demonstrate the ability of the phototherapy kiosk to safely administer UVB radiation to participants with sufficient or insufficient levels of 25(OH)D and achieve comparable levels of serum 25(OH)D in a similar population of adults randomized to receive the RDA of 600 IU vitamin D oral supplementation once daily. As an experimental device, it is important to evaluate its equivalence to standard of care in the maintenance of sufficient levels of vitamin D in adults with all skin types between 18 and 69 years of age. In this study the supplement group (CG) was used as an active control.

6.3 Selection of Study Population

Inclusion and exclusion criteria are identical for both groups, supplementation (CG) and phototherapy (TG).

6.3.1 Inclusion Criteria

- Adults, age 18 - 69 years
- Ability to read and understand English
- Subjectively in good health

- Able to stand without assistance for ~10 minutes

6.3.2 Exclusion Criteria

- Any volunteer with relocation, deployment, or release from active duty in the next 4 months
- Pregnant, or currently breastfeeding, females
- Anyone with chronic health problems (e.g. kidney disease, liver disease, intestinal malabsorption)
- Any volunteer currently taking vitamin D supplementation
- Taking medications for an endocrine disorder, such as Synthroid or oral hypoglycemic agents
- Sarcoidosis
- Medications having a high potential for interaction with vitamin D:
 - anti-seizure medications, cyclosporine, indinavir (Crixivan)
- Adults diagnosed with light allergies:
 - Actinic prurigo, Polymorphous light eruption, Solar urticaria
- Adults diagnosed with light sensitivities:
 - Protoporphyrinia, Photodermatitis, Xeroderma pigmentosum, Lupus erythematosus, Actinic dermatitis, UV-sensitive syndrome

6.3.3 Removal of Patients from Therapy or Assessment

Participants enrolled in the study are free to withdraw at any time without repercussions; the study team requested to be informed in writing of their decision to withdraw.

Volunteers are reminded that the Principal Investigator of the research study may terminate their participation in the research study at any time if she determined this to be in their best interest, if they are unable to comply with the procedures required, or if they no longer meet eligibility criteria.

6.4 Treatments

6.4.1 Treatments Administered

Comparison Group - Supplement

Volunteers assigned to this group are provided with a 10-week supply (70 pills) of a vitamin D3 supplement. Consented participants are instructed to take one 600 IU pill by mouth each day for ten weeks. They are instructed to take this with a meal. This dose is the RDA for adults between 18 and 69 years old according to the Institute of Medicine Committee to Review Dietary Reference Intakes for Vitamin D and Calcium.²⁰

Treatment Group - Phototherapy

Volunteers assigned to this group are administered phototherapy treatments once every other week, for 10 weeks. The treatment usually lasts no more than 10 minutes and is based on the Fitzpatrick skin type classification tool¹⁹ which is self-assessed via the computer touch screen in the kiosk.

Table 1. Study Summary

Phase	Initial (T)	Time 1 (T+1wk)	Time 2 (T+3wk) Time 3 (T+5wk) Time 4 (T+7wk) Time 5 (T+9wk) Time 6 (T+11wk)	Time 7 (T+15wk)
Screening	X			
Informed Consent	X			
Submit Blood Tests	X		X (Time 6)	X
Randomization	X			
Demographics and Surveys		X	X (Time 6)	
Inbody		X		
Treatment -Phototherapy (every other week x6)		X	X (Time 6 = Final Exposure)	
Device Usability Scale - Phototherapy			X (Time 6)	
Treatment -Vit D Supplement (daily for 10 weeks)		X	X	

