All eligible adult volunteers will be enrolled regardless of their baseline 25(OH)D level as it is important in this non-inferiority study to show there is no potential for harm from phototherapy, even if the baseline 25(OH)D level is above 30 ng/mL. If the goal is to develop a self-care kiosk, individuals will not have the ability to check their serum vitamin D status prior to use. We also want to learn the trajectory of vitamin D absorption and availability over a 3-4-month period in order to make evidence-based therapeutic recommendations. It is not possible to blind the subjects or research team to the group assignment given the two comparators.

Serum levels of 25(OH)D, calcium, and parathyroid hormone are drawn at baseline (T0), immediately following the intervention at 10 weeks (T6); at 14 weeks (T8), 25(OH)D is drawn to document sustainment of treatment effect. Remuneration in the form of \$20 Amazon gift cards is provided to all volunteers after the baseline and final scheduled blood draw (as allowed by DoD Instruction 3216.02 Dated November 8, 2011).

A survey shall be completed at T1 and reviewed with participants again at the 10-week visit to capture relevant demographic, medical history, sun exposure, travel, daily activities, and dietary data. Active duty SMs shall report the number of days on profile (activity restriction) for the previous three months, at T1 and T6. A Device Usability Scale will be administered to the kiosk group participants upon protocol completion to address acceptability and feasibility of the treatment. With the assistance of a biostatistician, we will analyze data using repeated measures analysis of variance adjusting for significant covariates such as 25(OH)D level at baseline. Logistic regression analyses are used to predict outcomes and explain the interrelationships among variables, i.e. age, gender, BMI, body fat, ethnicity, and sun exposure relationship to 25(OH)D serum levels.

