6.4.4 Selection of Doses in the Study

Comparison Group - Oral Supplement Dosing

For this non-inferiority study, the logical choice for a comparison arm was the Recommended Daily Allowance (RDA) of 600 IU vitamin D for adults in the age range of 18-70 years old. The RDA was established by the Institute of Medicine (IOM) who identified clinically significant levels of circulating 25(OH)D (20 ng/mL) and then estimated the amount of dietary vitamin D required to reach this circulating level with minimal sunlight exposure. The RDA for vitamin D represents a daily intake sufficient to maintain bone health and normal calcium metabolism in 97.5% the population.²⁰

Treatment Group - Phototherapy Dosing

All patients shall be dosed at 0.6 MED at a distance of 12" from the light source for all treatments. This is consistent with dosing demonstrated to be effective at raising serum 25(OH)D without the risk of adverse events.^{26, 27} Treatments shall occur on a 14-day interval (+/- 24 hours), for a total delivery of 6 doses.

To obtain dose, each participant will self-assess their skin type according to the Fitzpatrick skin typing scale using software inside the kiosk. The kiosk will determine the dose per patient, based on their answers. Erythema response to the previous treatment dose is self-assessed. In the event erythema is self-reported via the kiosk, the participant's dose is reduced by the system for subsequent treatments.

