6.4.5 Selection and Timing of Dose for Each Patient

Comparison Group

Each participant assigned to the comparison group will be instructed to take one vitamin D3 pill each day with a meal for 70 days. Participants will also be instructed not to take any additional vitamin D supplementation during the study period. This dosing frequency is consistent with the RDA recommendation.²⁰

Treatment Group

Treatments shall occur on a 14-day interval (+/- 24 hours), for a total delivery of 6 doses. Each participant is informed of the need for consistency in the time of day for subsequent phototherapy treatments and every attempt will be made to ensure the participants return 14 days after each treatment for 10 weeks. This dosing frequency is consistent with the minimum recommended for Solius vitamin D therapy previously shown to be adequate in maintaining serum 25(OH)D levels.^{26, 27}

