6.4.8 Adherence

Comparison Group

Participants agree to oral administration of 600 IU vitamin D once per day. Participants must agree to abstain from ingesting oral vitamin D supplements. Participants must also have blood drawn at baseline, day 70, and at day 100.

Treatment Group

Participants must be exposed once every other week (14 days +/- 24 hours). Participants must agree to abstain from ingesting oral vitamin D supplements. Participants must also have blood drawn at baseline, day 70, and at day 100.

In this pilot feasibility study, one aim is to evaluate acceptability and adherence.

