6.5 Efficacy and Safety Variables

6.5.1 Efficacy and Safety Measurements Assessed

To determine that phototherapy is at least equivalent to D3 oral intake to raise or maintain serum 25(OH)D levels over a 10-week intervention period baseline 25(OH)D levels are obtained.

Blood draws will occur upon enrollment with two follow-up measurements, one at 10 weeks and a final level 4 weeks after completing the protocol to evaluate sustainment of the post-treatment level. Serum concentration of 25(OH)D is the best indicator of vitamin D status as it represents cutaneous production and consumption of food and supplements. Serum 25(OH)D has a circulating half-life of 15 days.²⁸ Serum 25(OH)D levels do not indicate the amount of vitamin D stored in body tissues.¹⁰ All blood levels will be obtained by experienced phlebotomists in the hospital central laboratory. There will be no standardization of time of day for the blood draw. An Endocrine consultant will review all abnormal lab values [(25OH)D, PTH, Calcium] and recommended follow-up with the Primary Care Manager, if necessary.

To determine acceptability and feasibility of the standing phototherapy kiosk, a Device Usability Scale will be administered to the Kiosk Group upon completion of the study. This 12-item Likert-type scale was adapted from the Digital Equipment Corporation "System Usability Scale" (1986). Questions assessed cleanliness, ease of use, and comfort of the kiosk with a Likert-type scale where 1= Strongly disagree to 5 = Strongly agree.

The research team will meticulously track the number of potential participants screened, the number of enrolled subjects, completion of all study timepoints, and attrition from each arm.

To examine the relationship of demographic variables, including gender, age, body mass index, body fat, ethnicity, and sun exposure to serum 25(OH)D levels in both groups, several other measurements will be obtained including the following:

1. Body height (Ht) – Vertical height is measured at baseline using a Harpenden Stadiometer and recorded to the nearest 0.1 cm. The stadiometer is composed of a rigid vertical backboard with an attached rigid horizontal headboard which moves up and down the backboard. Final height was the average of two measurements taken by trained study staff.

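### The Time 6 blood sample coincides with the sixth kiosk exposure, so the week-10 to week-14 change overstates how well the kiosk effect is sustained, while the week-10 comparison leans against the kiosk

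*Combined protocol and SAP*

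**What the plan says.** The kiosk schedule in section 6.4.4 is "Treatments shall occur on a 14-day interval (+/- 24 hours), for a total delivery of 6 doses", and section 6.4.5 repeats the count. Table 1 (section 6.4.1) starts exposures at Time 1 (T+1 week) and marks Time 6 (T+11 weeks) as "X (Time 6 = Final Exposure". The blood-test row of the same table also has its post-treatment entry at Time 6. The comparison arm receives "a 10-week supply (70 pills) of a vitamin D3 supplement", one to be taken each day.

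Section 6.1 places the second and third samples as "immediately following the intervention at 10 weeks (T6); at 14 weeks (T8), 25(OH)D is drawn to document sustainment of treatment effect". Section 6.5.1 describes the last sample as "a final level 4 weeks after completing the protocol to evaluate sustainment of the post-treatment level". Section 6.4.8 gives days instead of weeks: "Participants must also have blood drawn at baseline, day 70, and at day 100".

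No section gives the order of draw and exposure at Time 6, or a lag between them. Section 6.5.1 leaves the time of day of the draw open. The analysis named in section 6.1 is a repeated-measures analysis of variance adjusting for covariates such as baseline 25(OH)D. Section 6.5.3 names serum 25(OH)D as the primary endpoint without a time point; week 10 is inferred from the ten-week period in aim 2 (section 5).

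**The concern.** A sample taken at the visit of the last exposure can show little of that exposure. The kiosk arm's post-treatment level is then a trough, about 14 days after the last exposure that can have had much effect, while the pill arm is sampled at the end of daily dosing. The sixth exposure acts during the following four weeks. It therefore raises the kiosk arm's final level without having raised the level from which decline is measured.

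The two readings are pushed in opposite directions. At week 10 the kiosk looks weaker than its six-exposure course. From week 10 to week 14 it appears to hold its level better than pills, even if 25(OH)D from the two routes decays identically. Section 6.1 says the team wants the trajectory over 3-4 months in order to make therapeutic recommendations, so an artefact in that trajectory could be read as longer persistence of skin-made vitamin D.

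**Working it through.** **Inputs from the protocol.** Six exposures 14 days apart (6.4.4, 6.4.5); last exposure and post-treatment blood test both at Time 6 (Table 1); 70 daily pills (6.4.1); 15-day half-life of 25(OH)D (6.5.1); final draw 4 weeks later (6.5.1), or day 100 (6.4.8).

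**Assumptions.** First-order decay, linear response, the same decay in both arms, blood drawn before the exposure unless stated. Day 0 is Time 1 and pills fall on days 0-69. Each exposure adds one unit to the rise above baseline.

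**1. The plan's own count.** 70/14 + 1 = 6 exposures, on days 0, 14, 28, 42, 56 and 70, that is T+1, 3, 5, 7, 9 and 11 weeks. The schedule reproduces, and the sixth exposure falls on day 70.

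**2. Kiosk rise at day 70.** Sum of 0.5^((70-d)/15) for d = 0, 14, 28, 42, 56: 0.039 + 0.075 + 0.144 + 0.274 + 0.524 = 1.056. With the sixth exposure fully counted it would be 2.056, so the draw shows 1.056/2.056 = 51% of it.

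**3. Apparent retention at day 98.** The decay factor over 28 days is 0.5^(28/15) = 0.274.
- Kiosk: 2.056 × 0.274 = 0.564, and 0.564/1.056 = 53%.
- Pills: nothing is added after day 69, so 27%.
- Kiosk without the sixth exposure: also 27%.
- Share of the kiosk's final rise due to the sixth exposure: 0.274/0.564 = 49%.

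At day 100 the factor is 0.25, giving 49% against 25%. Retention compares each arm with itself, so it does not depend on how pills are equated to exposures. With assumed half-lives of 12, 20 and 25 days it is 45, 64 and 72% for the kiosk against 20, 38 and 46% for pills.

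**4. Gradual conversion.** The protocol gives no conversion time. With an assumed conversion half-time h, a dose contributes ka/(ka-k) × (e^(-ku) - e^(-ka·u)) after u days, where k = ln 2/15 and ka = ln 2/h.

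**5. Week-10 shortfall.** Two ways of equating the arms: (A) 70 pills equal six exposures, 6/70 unit per pill; (B) 14 pills equal one exposure, 1/14 unit per pill. With instant conversion the day-70 pill rise under A is 6/70 × 20.31 = 1.741, or 1.823 if each pill is credited a day later. The shortfall is 1 - 1.056/1.741 = 39% to 1 - 1.056/1.823 = 42%. Under B the pill rise is 1.451 to 1.519, and the shortfall 27-30%.

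| Assumed conversion half-time | Retention, kiosk / pills | Week-10 kiosk shortfall, A / B |
|---|---|---|
| Instant | 53% / 27% | 39-42% / 27-30% |
| 1 day | 53% / 29% | 36% / 23% |
| 3 days | 55% / 34% | 28% / 14% |
| 7 days | 66% / 46% | 21% / 6% |

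**6. Draw after the exposure.** For a draw 3 hours later and h of 1-7 days, the sixth exposure supplies only 1-7% of the measured rise, and retention is 50-66% against 29-46%. With h = 1 day, a draw 3 days later gives 34% against 32%, and by 7 days both are 38%. With slower conversion a gap remains.

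**7. Level at the final draw.** Instant conversion: under A, 0.564/0.477 = 1.18, or 0.564/0.500 = 1.13 with pills credited a day later; under B, 0.564/0.398 = 1.42. With h = 7 days: 0.901/0.799 = 1.13 under A and 0.901/0.666 = 1.35 under B. Across the settings tried with pills on days 0-69, the kiosk stands 13-42% above pills at the final draw although decay is identical.

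**The case against.** Several objections have force.

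- *No retention measure is planned.* The protocol says why the last sample is drawn, but defines neither a change from week 10 nor a percentage retained, and section 6.6.1 calls the analyses exploratory. That is correct. Still, both descriptions of the last sample refer back to the level after treatment, and a group-by-time effect in the repeated-measures analysis would contain this contrast. It is better settled before anyone reads it.
- *The week-10 effect is not a threat.* It works against the kiosk, so it cannot by itself produce a false finding of non-inferiority, and an end-of-interval level is a legitimate measure of a fortnightly regimen. This stands. Five 14-day intervals also span the full 70 days, so the issue is an uncounted last dose, not a shorter course.
- *Same-day sampling is inferred.* Time 6 is a week label and blood is drawn in the central laboratory with no stated window. A draw several days after the exposure would shrink the gap, or remove it if conversion is fast. This stands, and it is why the order must be stated.
- *The final-draw difference also favours the kiosk.* It does in this model, by 13-42%, because a whole exposure lands on the last day while pills are spread over ten weeks. It remains a valid randomised comparison of two complete regimens, but not a neutral measure of persistence.

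A reader might also infer that the sixth exposure cannot appear at all in a same-day sample. The protocol gives a half-life but no conversion time, so only the weaker statement, that it barely appears unless conversion is near-instant, is supported.

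**Conclusion.** The point holds for the change from week 10 to week 14. If the draw precedes the exposure or falls on the same day, that change is biased in the kiosk's favour: 53% against 27% retained under the plan's half-life with instant conversion, and 53-66% against 29-46% with assumed conversion half-times of 1-7 days and the draw first. The direction held at every half-life tried and for a draw three hours after the exposure. The sizes are illustrative; they rest on linear response, equal decay and assumed conversion times.

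At week 10 the comparison is conservative for the kiosk, by about 6-42% of the increment depending on the model. A reader might take the upper end, 39-42%, as the size of the deficit, or conclude that the primary comparison is tilted towards the kiosk. The documents support neither: the upper end needs instant conversion and one particular equating of pills to exposures, and the direction is the reverse. That week 10 is the primary time point is itself an inference.

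If day 70 is counted from the initial visit T, it falls between Time 5 (T+9 weeks, day 63) and Time 6 (T+11 weeks, day 77). That is still five exposures, but only about 70 - 7 = 63 pills.

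**What to change.** No visit, draw or exposure needs to move.

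1. State in Table 1 and section 6.5.1 whether blood at Time 6 is taken before or after the exposure, and describe the week-10 kiosk result as the level before the sixth exposure takes effect.
2. Do not interpret the change from Time 6 to the final draw, or the matching group-by-time contrast, as sustainment or slower decline. Report instead the baseline-adjusted between-arm difference at the final draw, described as a comparison of the two complete regimens about four weeks after last treatment. Note beside it that a full exposure on the last day raises the kiosk level there, so that the difference is not evidence of longer persistence.
3. Report the arm differences at both draws side by side.
4. Reconcile sections 6.1, 6.4.1, 6.4.5, 6.4.8 and 6.5.1: six doses against a sample described as following the intervention, days 70 and 100 against weeks 10 and 14 (14 weeks is day 98), the origin from which days are counted, and T8 in section 6.1 against Time 7 in Table 1.

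The cost is wording and one analysis definition; baseline adjustment is already foreseen in section 6.1. What is given up is the simple comparison of decline from week 10.

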6.4.2 Identity Investigational Product

The Solius phototherapy device (SOLIUSOne, Serial# 00102) is intended for use in the stimulation of endogenous vitamin D. Solius is a freestanding booth designed to deliver a small amount of targeted UVB with an interactive user interface and cloud-based software that enables patient self-care. The treatment delivery mechanism uses a metal halide lamp with a series of filters and a lens to optimize full-body exposure to the narrow spectrum (293 – 303nm) of UVB light most efficient at producing vitamin D3. The device uses software to identify patients, establish individual skin types and determine dosage. The system has been designed to manage exposure time and frequency and deliver 60% of a skin-type-adjusted Minimal Erythema Dose (MED). The expected result for users is a rise in blood levels of 25(OH)D via the endogenous pathway.¹³

6.4.3 Method of Assigning Patients to Treatment Groups

A computer-generated block design will be created by an onsite biostatistician and used by the research pharmacist to randomize participants. Upon meeting the inclusion criteria, the pharmacist will be notified of the new participant and she will relay the assigned group to the team. The study team will have had no knowledge of the group assignment in advance.

6.4.4 Selection of Doses in the Study

Comparison Group - Oral Supplement Dosing

For this non-inferiority study, the logical choice for a comparison arm was the Recommended Daily Allowance (RDA) of 600 IU vitamin D for adults in the age range of 18-70 years old. The RDA was established by the Institute of Medicine (IOM) who identified clinically significant levels of circulating 25(OH)D (20 ng/mL) and then estimated the amount of dietary vitamin D required to reach this circulating level with minimal sunlight exposure. The RDA for vitamin D represents a daily intake sufficient to maintain bone health and normal calcium metabolism in 97.5% the population.²⁰

Treatment Group - Phototherapy Dosing

All patients shall be dosed at 0.6 MED at a distance of 12" from the light source for all treatments. This is consistent with dosing demonstrated to be effective at raising serum 25(OH)D without the risk of adverse events.^{26, 27} Treatments shall occur on a 14-day interval (+/- 24 hours), for a total delivery of 6 doses.

To obtain dose, each participant will self-assess their skin type according to the Fitzpatrick skin typing scale using software inside the kiosk. The kiosk will determine the dose per patient, based on their answers. Erythema response to the previous treatment dose is self-assessed. In the event erythema is self-reported via the kiosk, the participant's dose is reduced by the system for subsequent treatments.

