Endogenous production of vitamin D comes from sun exposure, however concerns of skin cancer and heat injuries limits recommendations for even a safe level of exposure. The only alternative has been consumption of vitamin D supplements, yet there is a paucity of evidence for how often, how much, and for how long one should consume supplements. Unlike endogenous vitamin D, research shows that supplements do not bind completely to vitamin D binding protein and are not regulated in the body to prevent overdose.³²⁻³⁵ Fat malabsorption conditions (cystic fibrosis, Crohn's disease, celiac, liver disease, etc.) can reduce the ability to absorb fat soluble vitamin D supplements yet endogenous vitamin D production from UVB light is uninhibited.^{2,36-40} UVB radiation with a wavelength of 290-320 nm penetrates the exposed skin and converts cutaneous 7-dehydrocholesterol to pre-vitamin D3, which in turn becomes vitamin D3. Maximal immune system response occurs at a peak of 300 nm and vitamin D3 production at a peak of 298 nm.³ Sunlight exposure provides 80-100% of the body's vitamin D requirements. Factors that influence UVB exposure and vitamin D synthesis include season, time of day, length of day, cloud cover, smog, skin melanin content, and sunscreen. However, a simple "prescription" for midday sun exposure under a cloudless sky with 90% skin exposure and no sunscreen in a non-urban, minimally polluted environment is a challenge for almost every American, and even more so for Service Members.

The current standard of care is 600 IU oral vitamin D daily, which is the RDA established by the Institute of Medicine (IOM) who identified clinically significant levels of circulating 25(OH)D to be 20 ng/mL. The RDA for vitamin D represents a daily intake sufficient to maintain bone health and normal calcium

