6.1 Overall Study Design and Plan

This non-inferiority study used a prospective, longitudinal, randomized design with repeated measures to address vitamin D sufficiency in AD, retiree, beneficiary, and DA civilian populations. It is important and necessary to conduct this study with adult humans, military personnel in particular, to determine acceptability and feasibility of this phototherapy kiosk as an addition to existing Warfighter resources to promote health and resilience. Following Madigan Army Medical Center (MAMC) Institutional Review Board Human Subjects and Ethics approval, the SPK will be installed in a location approved by the Radiation Safety Officer, the study team will be hired, and recruitment will begin for an anticipated 12-month project period. Approximately 120 volunteers will be approached from MAMC and Joint Base Lewis-McChord (JBLM), a large joint base in the Pacific Northwest, where over 25,000 Soldiers and Airmen train every day and regional beneficiaries' number ~98,000. Recruiting efforts will attempt to capture a representative sample of the population including both genders, diverse ethnicities, and a range of age (18-70 years) and body mass index (BMI), who have no contraindication for UVB exposure or oral vitamin D supplementation. In addition to walk-in volunteers, the research team will attend the JBLM Newcomer's Orientation. Using a computer-generated block design, volunteers will be randomized to one of two groups by the research pharmacist; 1) oral vitamin D supplementation, or 2) standing phototherapy kiosk with UVB exposure, for a 10-week period.

Comparison Group (CG) – Supplement

A MAMC research pharmacist will dispense a 70-day supply of the vitamin D3 600 IU oral supplement to subjects assigned to this group. The Project Director will work with the pharmacist to coordinate pick-up of supplement bottles for subjects or optimal in-person dispensing times.

Treatment Group (TG) – Phototherapy

The Project Director provides oversight for the phototherapy treatment. The kiosk will deliver the UVB dose under supervised conditions over a 1 – 10 minute interval based on the Fitzpatrick skin type with the subject wearing minimal or no clothing, preferably no more than a bathing suit, and protective eye-wear. The experience in the SPK was designed to be comfortable and user-friendly.

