6.4.7 Prior Concomitant Therapy

Other medications are allowed except those listed in the exclusion criteria (anti-seizure medications, cyclosporine, and idinavir). The research pharmacist will provide expertise for establishing screening criteria to eliminate any potential drug-drug or drug-nutrient interactions. No attempt will be made to control for sun exposure or dietary intake of vitamin D, however, all participants are instructed to refrain from taking any additional supplements containing vitamin D. Volunteers will be asked about vitamin D supplementation during screening and anyone taking a vitamin D supplement in the previous 2 months will not qualify for the study. Both amount of sun exposure and consumption of dietary vitamin D will be captured on surveys. Logistic regression analyses will be used to predict outcomes and explain the interrelationship among the two variables (i.e. sun exposure relationship to 25(OH)D serum levels).

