6.5.3 Primary Efficacy Variable(s)

Serum 25(OH)D level is the primary endpoint used to establish whether the treatment in the phototherapy kiosk group is equivalent to the oral vitamin D3 supplementation currently prescribed as the standard of care. It is expected that the serum 25(OH)D levels in both groups will rise over time and that the serum 25(OH)D levels will be equal to, or not less than, that of the oral supplementation group.

A Device Usability Scale will be administered to the Kiosk Group to assess acceptability and feasibility. This 12-item Likert-type scale was adapted from the Digital Equipment Corporation

“System Usability Scale” (1986) and it will be administered to the Kiosk Group upon completion of the study.

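### With sun uncontrolled and no untreated arm, a rise in both groups cannot be credited to treatment, and season has no stated place in the arm comparison

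*Combined protocol and SAP*

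**What the plan says.** - **Control dose.** Section 6.4.4 takes 600 IU from the RDA. It explains that the Institute of Medicine identified 20 ng/mL as the relevant level and "estimated the amount of dietary vitamin D required to reach this circulating level with minimal sunlight exposure".
- **Sun in the trial.** Section 6.4.7: "No attempt will be made to control for sun exposure or dietary intake of vitamin D". The same section adds: "Both amount of sun exposure and consumption of dietary vitamin D will be captured on surveys". Section 6.1 has the survey completed at T1 and reviewed at 10 weeks.
- **Weight given to sun.** In the Introduction (section 4), the sentence that opens "Sunlight exposure provides 80-100% of the body" concerns vitamin D requirements. The next sentence names season among the factors that influence synthesis.
- **Arms and calendar.** Section 6.1: "volunteers will be randomized to one of two groups by the research pharmacist", namely supplement or kiosk. Section 6.2 calls the supplement group an active control. Section 6.1 anticipates a 12-month project and enrols whatever the baseline 25(OH)D. The title page dates run from 21 August 2017 to 11 March 2019.
- **Analysis.** Section 6.1 plans "repeated measures analysis of variance adjusting for significant covariates such as 25(OH)D level at baseline", and logistic regression to "explain the interrelationships among variables, i.e. age, gender, BMI, body fat, ethnicity, and sun exposure relationship to 25(OH)D serum levels".
- **Expected result.** Section 6.5.3: "It is expected that the serum 25(OH)D levels in both groups will rise over time". The sentence goes on to expect kiosk levels equal to or not below those on supplement. No margin is given.

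**The concern.** A non-inferiority result says something about a new treatment only if the control has an effect under the conditions of the trial. The plan's argument for 600 IU concerns minimal sunlight. The trial's conditions are whatever sun participants get over a year or more, at any starting level. No arm shows what happens with neither treatment.

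Two conclusions are exposed. First, Aim 2 speaks of raising or maintaining 25(OH)D, and section 6.5.3 expects both groups to rise. Spring and summer sun could produce that rise with no help from either treatment. Second, if 600 IU adds little in sun-exposed or replete adults, a kiosk with no effect would lie close to the control and could be called non-inferior.

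**Working it through.** **The plan's own figure.** Section 6.6.2 gives 60 required, 30% dropout and a minimum of 78. This reproduces as 60 × 1.30 = 78. The 60 cannot be rebuilt, because no margin, SD, alpha or power is stated. Only the 60 is used below: 30 per arm, assuming equal allocation.

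**Assumed inputs (none is in the documents).** SD 6 to 8 ng/mL, margin 5 ng/mL, one-sided 2.5%, noncentral t.

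**Step 1: does sun by itself favour an inert kiosk?** Let sun add the same mean amount S in both arms and let 600 IU add E. With an inert kiosk the arm difference is (S + 0) − (S + E) = −E, so S cancels. Sun that varies between people only widens the SD. Take E = 4 and SD 8: the standard error is 8 × √(2/30) = 2.07, the noncentrality is (5 − 4)/2.07 = 0.48, and the chance of passing is 6.9%. If sun adds an SD of 6, the total SD is √(64 + 36) = 10, the noncentrality is 0.39, and the chance is 5.7%. Additive sun does not help the kiosk pass.

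**Step 2: what if sun or a replete baseline shrinks E?** For an inert kiosk the noncentrality is (5 − E)/(SD × √(2/30)), where √(2/30) = 0.258.

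| E, what 600 IU adds (ng/mL) | SD 6 | SD 8 |
|---|---|---|
| 5 | 2.5% | 2.5% |
| 2 | 48% | 30% |
| 1 | 72% | 48% |

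The first row follows from setting the margin equal to E. The other rows arise because the margin then exceeds the control's effect. They illustrate the mechanism and do not estimate what happens at this site.

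**Step 3: within-arm reading.** Suppose neither treatment works and season lifts everyone by 4 ng/mL. In a paired test with 30 per arm, reading the SD as the SD of change, the noncentrality is 4/(SD/√30) = 3.65 at SD 6 and 2.74 at SD 8. The rise is significant 94% and 75% of the time. Season can equally lower levels in participants who start in late summer, so the direction is not fixed.

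**Step 4: where could the plan deal with season?** Baseline 25(OH)D is the only covariate named for the repeated measures model. Sun exposure appears in the regression on relationships (sections 6.1 and 6.4.7, serving Aim 3). Section 6.4.3 describes a block design without a season stratum. No section puts season or draw date into the arm comparison.

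**Step 5: precision of a low-sun subset.** If half the participants fall in low-sun months there are 15 per arm. The half-width is 2.048 × SD × √(2/15) = 0.748 × SD, or 4.5 to 6.0 ng/mL, against 0.517 × SD, or 3.1 to 4.1, with 30 per arm. For the arm-by-season difference, with four cells of 15, it is 2.003 × SD × √(4/15) = 1.034 × SD, or 6.2 to 8.3 ng/mL.

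**The case against.** The strongest reply is that the arms are randomised concurrently, so sun is balanced on average and the between-arm difference is protected. That stands for an additive sun effect, as Step 1 shows. A reader might infer from the uncontrolled sun that the design itself lets a weak kiosk pass. The documents do not support that: it happens only if sun or a replete baseline reduces what 600 IU adds, and no section says so or gives a size.

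Other points also have force.

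- Sun is recorded by survey and analysed, and the covariate list is open-ended. This is a partial answer: the record is self-reported, no calendar term is named, and no covariate can replace an untreated reference.
- The Introduction says adequate midday sun is hard to get for nearly all Americans and more so for Service Members, and the site is in the Pacific Northwest. Trial conditions may therefore be closer to minimal sunlight than the 80-100% statement suggests.
- Section 6.5.3 states the rise as an expectation, and Aim 2 is comparative. A seasonal rise therefore misleads only if within-arm change is read as effect.
- This is a pilot whose stated question is comparability with standard of care under ordinary conditions. Enrolling through the year is defensible for that.

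A reader might also infer that the Aim 2 claim should depend on the low-sun subset. That goes too far. Under the same assumptions a truly equal kiosk passes with 15 per arm only 60% (SD 6) to 38% (SD 8) of the time, against 89% to 66% with 30 per arm. The condition would therefore block a fully equal device 40% to 62% of the time, and the subset would still lack an untreated arm.

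**Conclusion.** The concern holds in a limited form. The mismatch is in the text: a control dose argued for minimal sunlight, sun left uncontrolled over about 12 months, no untreated arm, and no season or draw-date term in the arm comparison. It follows that a rise in both arms cannot be credited to either treatment. It also follows that non-inferiority to 600 IU would show that the kiosk works only if 600 IU itself has an effect in this setting, which the plan does not demonstrate.

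The size is uncertain. The 75% to 94% chance of a significant seasonal rise and the 30% to 72% chance of an inert kiosk passing (when 600 IU adds 1 to 2 ng/mL) rest on an assumed SD, margin and effect. The second range also reflects the absence of a stated margin, which is a separate gap. The documents do not show that sun biases the between-arm difference, nor that a year-round comparison is uninformative for Aim 2.

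**What to change.** Add three statements to section 6.6.1.

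1. The Aim 2 conclusion rests only on the between-arm difference. Change within an arm will not be read as treatment effect, because there is no untreated reference.
2. Calendar season of the blood draw is a prespecified term in the between-arm model. Because randomisation already balances season on average, the main gain is in precision and in protection against chance imbalance.
3. As supportive evidence, and not as a condition for the claim, report the arm difference in participants whose Time 1 to Time 6 window falls in low-sun months. Fix those months before analysis and assign participants by randomisation date. Report the arm-by-season difference with its confidence interval beside it.

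This costs SAP wording and one extra analysis, using only dates that the trial holds. The downside is imprecision: a half-width of about 4.5 to 6.0 ng/mL for the subset and 6.2 to 8.3 ng/mL for the arm-by-season difference, at an assumed SD of 6 to 8. The subset does not by itself establish assay sensitivity, and the report should say so. The title page carries a completion date; if results by arm have already been seen, items 2 and 3 should be labelled post hoc.
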